CONNECT. For sites randomized to REP + CONNECT, sites will receive explicit training and instruction prior to iHI-FIVES program delivery targeted to CSCs and other services about the benefits of interacting together to improve CG support. Currently there is sub-optimal information flow directly between providers (social workers, CSCs, PACT nurses) that is then communicated back to patients and their CGs. We anticipate CONNECT to facilitate more direct information flow between the diverse providers that serve CGs and their Veterans with cognitive and/or functional impairment, which will thereby improve the success of iHI-FIVES implementation. Because the potential team members in iHI-FIVES (e.g. VAMC personnel who support caregivers) often work in different locations without regular opportunities for frequent communication, the Group and Individual Mapping components of CONNECT will likely be the focus of their team training (Relationship Mapping, Table 1). Land-scape site-visits and close coordination with the implementation core will be used for optimal adaptation of CONNECT for iHI-FIVES.

All activities related to implementation of iHI-FIVES as described above are non-research operations activities, as defined in VHA Handbook 1058.05. These programs are designed to support VHA's mission of delivering health care to the Nation's Veterans.

		Recruitment months						
Stratified Block	Wave	1-6	7-12	13-18	19-24	25-30		
1	1							
1	2							
2	1							
2	2							
■ pre-implementation ■ post-implementation ■ administrative data collection only								
Figure 5: Stepped wedge design for the 8 participating VAMCs								

Study timeline. In this stepped-wedge design, iHI-FIVES implementation will occur in two stratified blocks (4 VAMCs per block) with two waves per block (2 VAMCs per wave), with each wave corresponding to a different 6 month period to begin offering the iHI-FIVES training to CGs in each study site (Figure 5). The timeline for HI-FIVES will be 30 months in which pre-implementation (control) and post-implementation (treatment) data will be collected. In this design, each cluster (VAMC) provides before (control) and after (interven-

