To address the impact of the iHI-FIVES program, we will use quantitative methods to examine the effect on patient outcomes. The overall anticipated number of eligible Veteran patients in the iHI-FIVES study will be 15,000-18,000 total patients. The analysis plan of our primary outcome is to examine days at home for the patient over a 6-month interval and will be defined as the total number of days not in the emergency department, nursing home, or inpatient ward. The start date for each patient, or the day of the automated data pull, will be "day 0" for all patients, and the maximum total possible number of days at home will be 180 for all patients. To make this outcome variable easier to deal with analytically, our first step will be to calculate each patients' days not at home by subtracting their number of days at home from 180, converting the "stack" of days at 180 to a "stack" at zero. For days not at home outcome, we anticipate, that it may have an excess of zeros and larger variance than what is to be expected from either a Poisson or Negative Binomial process. Common approaches for analyzing this type of data are the zero-inflated Poisson (ZIP) model and the zero-inflated negative binomial (ZINB) model¹¹⁶ or two-part models.^{117,118} Consequently, we will explore the distribution that best fits this outcome: Poisson, Negative Binomial, ZIP, ZINB, or a semi-continuous distribution such as a two-part gamma.¹¹⁹

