Sample size estimate. For STRIDE, sample size calculations were conducted for patient-level analyses evaluating impact of STRIDE on discharge to skilled nursing facility. The sample size calculation was done based on a complete stepped-wedge design using Hussey and Hughes (2007) method.⁶⁰ The sample size is based on the following assumptions for the discharge to skilled nursing facility outcome: 1) base discharge rate to skilled nursing of approximately 20%; 2) 10% drop in discharge rate after STRIDE, determined as a clinically significant gain in the outcome; 3) intracluster correlations (ICC) ranging from 0.02 to 0.6 for patients within the same hospital; 3) 8 hospital sites with 5 3-month assessment periods; and 4) alpha=0.05, power>80%. A total sample of 2000 patients (~250 per hospital, 50 per 3-month interval) will result in ≥80% power to detect a 10% reduction in discharges to skilled nursing facilities. The anticipated maximum sample is 16,000. For iHI-FIVES, the sample size calculation was done based on a complete stepped-wedge design using Hussey and Hughes (2007) method.⁶⁰ The overall anticipated number of Veteran patients will be 15,000-18,000 with a minimum sample size of 400 subjects (at least 50 per VAMC, 20 per 6-month interval). The power calculation for this sample size is based on the following assumptions for days not at home: 1) 8 is the baseline mean number of days not at home over 6 months; 2) 2-day reduction in days not at home over 6 months; 3) coefficient of variation (CV) ranging from 0.3 to 0.5 for assessments on participants within the same VAMC; 4) 8 VAMCs with five 6-month assessment intervals; and 5) alpha=0.05, power>80%. A minimum sample of 400 Veterans will result in at least 80% power to detect a mean reduction of 2 days not home assuming variance equal to the mean (Poisson distribution).

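### The iHI-FIVES minimum of 400 does not match its own 20 per interval, which implies 800, and its 80% power is shown for Poisson variance only

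*Combined protocol and SAP*

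**What the plan says.** The sample size paragraph (Analyses, Sample size estimate) uses the Hussey and Hughes method for a complete stepped wedge. For iHI-FIVES it gives "a minimum sample size of 400 subjects (at least 50 per VAMC, 20 per 6-month interval"), with "8 VAMCs with five 6-month assessment intervals". The inputs are a baseline mean of 8 days not at home, a 2-day reduction, a "coefficient of variation (CV) ranging from 0.3 to 0.5 for assessments on participants within the same VAMC", and alpha 0.05. It concludes that 400 Veterans give at least 80% power "to detect a mean reduction of 2 days not home assuming variance equal to the mean (Poisson distribution"). The anticipated number of patients is 15,000 to 18,000.

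The STRIDE sentence in the same paragraph has the same layout: "A total sample of 2000 patients (~250 per hospital, 50 per 3-month interval").

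The Aim 2b analysis text says of days not at home that "it may have an excess of zeros and larger variance than what is to be expected from either a Poisson or Negative Binomial process". It will choose among "Poisson, Negative Binomial, ZIP, ZINB, or a semi-continuous distribution such as a two-part gamma".

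Separately, the iHI-FIVES text on participating sites and on the sample of patients requires each site to have at least 50 recent referrals within a 3- or 6-month window.

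**The concern.** Two things look wrong. First, the total, the per-site number and the per-interval number in the stated minimum do not multiply out, so a reader cannot tell whether the floor is 400 or 800.

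Second, power at that floor is given only for a variance equal to the mean. A Poisson outcome with mean 8 has exp(-8) = 0.03% zeros, which is far from the stack at zero that the Aim 2b text describes. Of the candidate count distributions, Poisson is the one with the least variance.

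The two matter together. If the variance is two to four times the mean, the choice between 400 and 800 decides whether the floor still has 80% power.

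**Working it through.** **Sizes.** There are 8 x 5 = 40 VAMC-intervals.

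- 50 per VAMC: 8 x 50 = 400; 50 / 5 = 10 per VAMC-interval.
- 20 per VAMC-interval: 5 x 20 = 100 per VAMC; 8 x 100 = 800.
- 20 per interval over all sites together: 5 x 20 = 100 in total, which also misses 400.
- STRIDE: 50 x 5 = 250 per hospital; 250 x 8 = 2,000. This agrees, so per interval there means per hospital per interval.

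400 and 20 would fit together if each VAMC contributed 50 / 20 = 2.5 intervals on average. The paragraph instead specifies a complete design with five intervals, in line with the study timeline ("The timeline for HI-FIVES will be 30 months").

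**The plan's power figure.** The Hussey-Hughes variance of the effect is

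Var = I s² (s² + T t²) / [(IU - W) s² + (U² + ITU - TW - IV) t²]

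- I = 8 and T = 5. Two VAMCs cross at each of four steps. This is taken from the study timeline and the complete design, because Figure 5 is not shown.
- U = 20 exposed VAMC-intervals. W = 0 + 4 + 16 + 36 + 64 = 120. V = 2 x (16 + 9 + 4 + 1) = 60.
- IU - W = 160 - 120 = 40. U² + ITU - TW - IV = 400 + 800 - 600 - 480 = 120.
- s² = within-cell variance / patients per cell = 8 / 10 = 0.8.
- t = CV x 8 = 2.4 to 4.0, reading the CV as between-site.

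At t = 2.4: Var = 6.4 x 29.6 / (32 + 691.2) = 189.44 / 723.2 = 0.262, SE 0.512.
At t = 4.0: Var = 6.4 x 80.8 / (32 + 1,920) = 517.12 / 1,952 = 0.265, SE 0.515.

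Power, two-sided 0.05, is Phi(2 / SE - 1.96) = 97.4% and 97.3%. The stated at least 80% is met. A direct generalised least squares calculation gives the same SEs.

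**Over-dispersion.** The documents give no SD, so the ratios below are assumed. Here the within-cell variance is 8 x ratio in every cell; ranges span CV 0.3 to 0.5.

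| Variance/mean | Power at 400 | Power at 800 |
|---|---|---|
| 1 | 97% | over 99.9% |
| 1.5 | 89% | 99% |
| 2 | 79-80% | 97% |
| 3 | 62-63% | 89% |

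The 80% limit is a ratio of 1.94 to 1.98 at 400 (SD 3.9 to 4.0) and 3.87 to 3.95 at 800 (SD 5.6).

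Exposed cells have mean 6 under the 2-day effect. If the ratio rather than the variance is held constant (8 x ratio in control cells, 6 x ratio in exposed cells), power at 400 is 84-85% at ratio 2 and 68-69% at ratio 3. The limit is then 2.23 to 2.28 at 400. Doubling the cell size doubles the tolerable ratio, so at 800 it is about 4.5 to 4.6.

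**Anticipated sample.** 15,000 / 40 = 375 per cell and 18,000 / 40 = 450 per cell. With the same variance in all cells, 80% power for a 2-day reduction holds to an SD of 24.1 to 24.4 and 26.4 to 26.7 respectively.

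**The case against.** The case on the other side is substantial, and most of it stands.

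- **The power claim is true as written.** Its Poisson condition is disclosed, and both 400 and 800 satisfy it. A reader might infer from the mismatch that the 80% is false; the recalculation shows that it is not.
- **The floor is remote from what is expected.** The outcome comes from administrative data pulls, and the anticipated number is about 37 to 45 times 400. A reader might infer that iHI-FIVES is underpowered. Nothing in the documents supports that.
- **The site criterion points to larger numbers.** Fifty referrals in every 6-month window would give 50 x 5 x 8 = 2,000, where 80% power holds to a ratio of about 9.7 to 9.9 with the same variance in all cells. This is an entry criterion, so assuming that the volume persists goes beyond the text. Still, a restated minimum should be consistent with it.
- **The Aim 2b wording is conditional.** It says the outcome may be over-dispersed and gives no figure. It does not contradict the power statement; it names a condition for which no power is given.
- **The ratio limits depend on how exposed cells are treated**, which is why both conventions are shown.

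The CV wording does not say whether 0.3 to 0.5 is between-site or individual-level. A Poisson with mean 8 fixes the individual CV at 1 / sqrt(8) = 0.354, so a range makes sense only between sites. On that reading, moving across the range changes power at 400 by at most about 2 points. It is an optional clarification, not an error.

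None of this reconciles 400 with 20 per VAMC per interval.

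**Conclusion.** The stated minimum is internally inconsistent, by a factor of two, on arithmetic alone. The 80% power at 400 is correct under Poisson variance, where it is about 97%, but the plan does not show how far it extends. It is lost at a variance/mean ratio of about 1.9 to 2.0, or 2.2 to 2.3 if the ratio is the same in control and exposed cells; at 800 the limits are about 3.9 and 4.5.

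These limits assume a two-sided test, equal cell sizes, a random intercept for VAMC only, a between-site CV, two VAMCs per step, and a normal test with no small-sample correction for eight clusters. The over-dispersion range is assumed, because the documents give no SD.

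The finding is about the stated floor. It does not call into question power at 15,000 to 18,000 patients, or the design or analysis. It is worth correcting because it is a published sample size figure for the primary iHI-FIVES outcome and the correction is cheap.

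**What to change.** 1. State one minimum with matching parts: either 400 = 50 per VAMC = 10 per VAMC per interval, or 800 = 100 per VAMC = 20 per VAMC per interval. Say how it relates to the 50-referral site criterion, which counts referrals within a 3- or 6-month window rather than over the whole study.
2. Restate power at that minimum over a short range, for example variance/mean ratios of 1, 1.5, 2 and 3 plus one zero-inflated case, and say how the variance is set in exposed cells.
3. Optionally, say that the CV of 0.3 to 0.5 is between VAMCs, if that is what was meant, and give the detectable difference at 15,000 to 18,000.

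The cost is one corrected sentence and one short table, with no new data and no change to design or analysis. The downside is that the stated power at the minimum will look less favourable once over-dispersion is shown.

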Office of Geriatrics and Extended Care (GEC) funded development and dissemination of STRIDE, investing more than \$350,000 to date in the program. STRIDE was developed with support from VHA Office of GEC, as part of its Transformation to the 21st Century Non-institutional Long Term Care (T21 NILTC) initiative. As part of its evaluation of the NILTC program, GEC identified limited clinical resources and difficulty hiring new clinical staff as the major barriers to implementation of new programs. Thus this partnership was very influential in Function QUERI's choice of implementation strategies that focus on providing options for tailoring clinical programs and providing options for using existing clinical resources. A major priority for GEC is disseminating programs that have been developed through the T21 NILTC initiative; thus the knowledge gained about implementation strategies will be of immediate use and value to GEC. GEC will assist Function QUERI in recruiting sites for STRIDE participation, and also providing access to data through the GEC Data Analysis Center.

VA Caregiver Support Program (CSP) is committed to the implementation of iHI-FIVES and advising on all program projects. This partnership is critical to perform the work, because [name] will seek volunteer sites from the field, and will also provide data on caregivers enrolled in the CSP. Importantly, the CSP is dedicating tangible support of a 1.0 FTE Caregiver Support Coordinator ([name]) for four years to aid in Project 3 for training the team to deliver HI-FIVES, strategizing with sites on recruitment preferences, and providing ongoing phone and in-person support (see letter of support from [name]). Findings from HI-FIVES in Project 3 are critical to CSP, as the Office considers further expansion of HI-FIVES caregiver training programs and foci.

Physical Medicine and Rehabilitation (PM&R) Services are provided in a variety of settings including acute medical, surgical, and psychiatric units, and community living centers (CLC), with a goal of facilitating Veterans' ability to remain in the most independent and least restrictive living environment through therapeutic interventions. PM&R operates from a physician directed, interdisciplinary team-based model of care designed to increase independence and improve quality of life for Veterans with disabilities, which is directly aligned with the goals and focus of Function QUERI. PM&R leadership will provide important clinical and operational input on STRIDE and Group PT and will assist in recruiting sites for STRIDE.

Office of VA Voluntary Services (VAVS) coordinates activities for more than 140,000 volunteers who provide more than 11 million hours of service to America's Veterans. [name], National Director, will serve on the Advisory Board for Function QUERI. She is actively working with [name] and [name], Director of Voluntary Services at the Durham VAMC to develop a volunteer-based walking program in Durham that will serve as a model for other facilities that want to use volunteers.

VA Mid-Atlantic Healthcare Network (VISN 6). Network Director [name] has directed all medical centers in VISN 6 to develop a STRIDE program and has asked [name] and the Function QUERI team to lead this 2040 Function QUERI PI [name] AMD 23 5.17.2023 Page 30 of 42

effort. Drs. [name], [name], and [name] have experience working with VISN 6 leadership and medical centers conducting quality improvement projects.

With our Partners' input, we will seek commonality in the service delivery challenges facing VA providers' ability to serve vulnerable Veterans with impaired function and will work collaboratively to address these gaps. We will keep our national partners notified bi-annually regarding progress toward mutual implementation goals. We will also convene 3 in-person meetings in which national stakeholders and the QUERI program will share information to actively develop a short- and long-term vision of clinical and managerial processes in VHA to restore and sustain patient function and independence.

Veteran and Caregiver Engagement Panel. In addition to our close partnerships with clinical and operations stakeholders, the Function QUERI will engage a group of Veterans and caregivers throughout the projects. Our COIN has recently begun a Veterans Engagement Panel (co-led by [name]), and we have developed specific processes for identifying and involving Veterans meaningfully in this panel. The Function QUERI Panel will be based on those processes, as well as the experiences of the project leads with other patient stakeholder groups. The panel will have representation from key groups relevant to each of the projects (e.g., older Veterans with recent hospitalization, Veterans with knee OA, Veterans with recent referrals to home care services and their caregivers), as well as representation of women and minority Veterans. We expect the full panel will include about ten individuals. We will aim to convene the full panel twice annually (including one meeting during the first month of the funding period), and smaller panels will meet more frequently to advise on each specific project. The perspectives of this panel will be instrumental for bringing the Veteran and caregiver perspectives to all phases and aspects of the projects, including patient-centered outcomes (e.g., satisfaction measures), logistics of the clinical programs, and patient characteristics to include in analyses.

Program Timeline and Metrics. We propose a 5 year program of work for Function QUERI. Specific project and implementation core activities are outlined below. Key metrics will include initiation of Implementation Project 1 (STRIDE) and Local QI project 2 (Group PT for Knee OA) in Year 1, completion of a white paper on CONNECT and completion of Local QI project in Year 2, completion of implementation project 1 (STRIDE) in Year 4 and implementation project 3 (iHI FIVES) in Year 5. In Year 5 we will also synthesize and dissemination findings via a Team Building and Readiness Toolkit.

		YEAR 1			YEAR 2			YEAR 3				YEAR 4				YEAR 5				
	Quarter			r		Quarter			Quarter				Quarter			r	(Qua	irte	r
	1	2	3	4	1	2	3	4	1	2	3	4	1	2	3	4	1	2	3	4
Implementation Project 1: STRIDE																				
Train staff, draft intervention package, landscape site visits			¥																	
Baseline data collection																				
STRIDE implementation																				
Evaluation: surveys, interviews, and medical record review						V														ı.
Analyses, reports to partners, manuscripts																				
Local QI Project 2: Group PT for Knee OA																				
Group PT for Knee OA implementation			V																	
Evaluation: surveys, interviews			V																	
Analyses, reports to partners, manuscripts																				
Implementation Project 3: HI FIVES																				
Train staff, draft intervention package, landscape site visits																				
Baseline data collection																				
iHI FIVES implementation																				
Evaluation: surveys, interviews, and medical record review																				
Analyses, reports to partners, manuscripts																				
Implementation Core																				
Adapt CONNECT and prepare white paper			V																	
Implementation evaluation and analyses																				
Develop and disseminate Team Building and Readiness Toolkit																				

Privacy, Confidentiality, and Information Security

1. Lists of Data Reviewed and/or Collected for Screening/Recruitment and Conduction of Study:

Identifier(s)	Source(s) of Health Information
🔀 Names	Medical history & physical exam information
\boxtimes All geographic subdivisions smaller than a	Photographs, videotapes, audiotapes, or
State, including street address, city, county, pre-	digital or other images
cinct, and zip code. Describe: addresses to mail pa-	
tient and caregiver opt-out letters and written state-	
ment regarding the research. Zip code used to deter-	
mine rural-urban community area (RUCA) code and	
census tract will be used to determine Neighborhood	
Deprivation Index (NDI).	
\boxtimes All elements of dates (except year) for dates di-	Biologic specimens (e.g., blood, tissue,
rectly related to an individual, including birth date,	urine, saliva). Describe:
admission date, discharge date, visit or treatment	
dates, etc.; and all ages over 89, Describe: birth	
date, admission and discharge dates, referral dates, ED	
visit dates, date of enrollment	
I Telephone numbers	☑ Progress notes
E Fax numbers	Diagnostic / Laboratory test results
Electronic mail addresses (to email providers	Operative reports
study information and a survey link)	
Social Security Numbers	Imaging (x-ray, CT, MRI, etc.)
Medical record numbers	Discharge summaries
Health plan beneficiary numbers	Survey / Questionnaire responses
Account numbers	Billing records
Certificate and/or license numbers	HIV testing or infection records
Vehicle identifiers and serial numbers, including	Sickle cell anemia information
license plate numbers	
Device identifiers and serial numbers	Alcoholism or alcohol use information
Web Universal Resource Locators (URLs)	Drug abuse information
Internet Protocol (IP) address numbers	Mental health (not psychotherapy) notes
Biometric identifiers, including finger & voice	Psychological test results
prints	
Full-face photographic images and any compa-	Genetic testing
rable images	
\Join Any other unique identifying number, linked	U Other, describe:
study ID, characteristic, or code, describe: Study	
ID numbers	

The Personal Health Information that will be obtained, used, and/or shared for this study includes:

All non-Veterans enrolled in this study will receive the VA Notice of Privacy Practices (NOPP) and are requested to sign the acknowledgment form. The signed acknowledgment form will be maintained with the research records.

2. Data and/or Specimen Acquisition:

Data for this study will be collected through (*check all that apply*):

Prospective data and/or specimen collection obtained from participants. Provide description of processes:

Please see p. 11-14 in the protocol for a description of the data collection process for STRIDE. Please see p. 11-12 and p. 15-20 in the protocol for a description of the data collection process for iHI-FIVES.

Retrospective data collection and/or specimens obtained from medical chart review/data access. Describe how data will be obtained (e.g., fileman, CDW, etc.):

Please see protocol p.12-14 for a description of CDW, VistaWeb and medical chart review data collection for STRIDE and p. 15-19 for iHI-FIVES. Utilization data will be downloaded directly from national files to the Durham HSR&D COIN servers or the secure VINCI environment.

Retrospective data collection and/or specimens obtained from an IRB-approved data and/or specimen repository. Indicate the repository source including name, VA location, and IRB number:

Note: for data and/or specimens obtained from a VA approved data repository, a Data Use Agreement (DUA) must be executed prior to obtaining data and/or specimens. See VHA Handbook 1200.12 for further information.

3. Level of Data:

The following level(s) of data will be acquired/maintained for this study (check all that apply):

\boxtimes	Identified (e.g., names, addresses or other identifiers included)
\boxtimes	Coded (direct and/or all identifiers removed, but study code/ID included)
	De-Identified (all HIPAA 18 and study ID/code removed):
	Verified Statistically
	OR
	Verified by Absence or Removal of HIPAA 18 and study ID
	Limited Data Set

Other: Describe:

4. Location of Data and/or Specimens, and Data Retention Plan:

A. Data and/or Specimen Location: OITDURSQLRESCH.VA.GOV (SQL database server), \\OITDURHSMSMB601.va.gov\Durham_HSRD_R (shared document folder), and vhadurhsrdsas1.v06.med.va.gov (SAS server temporary storage).

Data will be stored electronically - See above. Data that will be stored electronically include - See protocol p. 10-19.

Paper records of data include participant study folders with records of enrollment dates, informed consent and any data collection instruments administered in paper form; will be stored in locked file cabinets (#129 6th floor), Legacy Tower.

Data will also be placed at the VA Informatics and Computing Interface (VINCI;

http://vaww.vinci.med.va.gov/vincicentral/VINCIWorkspace.aspx). The VA Informatics and Computing Infrastructure is a partnership between the VA Office of Information Technology and the Veterans' Health Administration Office of Research and Development. Researchers and operations staff can use VINCI to access data and statistical analysis tools in a virtual working environment through a certified VHA network computer using the VA Intranet or Virtual Private Network (VPN).

B. Data Retention Plan

Research records will be maintained and destroyed according to the National Archives and Records Administration, Records Schedule Number: DAA-0015-2015-0004. Records destruction, when authorized, will be accomplished using the then current requirements for the secure disposal of paper and electronic records. Currently, destruction of research records (see DAA-0015-2015-0004, section 7.6 "Research Investigator Files" for materials included in research records) is scheduled for 6 years after the cut-off (the cut-off is the completion of the research project) and may be retained longer if required by other federal agencies. Records will not be destroyed without pre-notification to the facility records manager.

Other data retention plan, describe:

5. Data Access and Data Recipients

All VA research personnel who have access to VHA records are instructed, in accordance with VA policy, on the requirements of Federal privacy and information laws and regulations, VA regulations and policies, and VHA policy. All study personnel who are VA employees working within the VA system have fulfilled all required HIPAA and other VA security and privacy policy training requirements and have agreed to follow guidelines pertaining to the protection of patient data. All research staff sign VA Rules of Behavior, and all study staff are up-to-date with VHA Privacy Policy Training and the VA Office of Cyber and Information Security Awareness Training Course. The data security and privacy procedures summarized in that course include logging off or locking the computer when walking away from it; no sharing of access codes, verify codes or passwords; not allowing anyone else to use the computer under one's password; and disposing of sensitive information using VA-approved methods (e.g., shredder bins).

Access to study data will be removed for all study personnel when they are no longer part of the research team.

6. Data and/or Specimen Transportation and/or Transmission for all data and/or specimens involved in the study:

- I. Data and/or specimens will not be transported or transmitted outside of Durham VAMC environment.
- II. Data and/or specimens will be transported BETWEEN sites that are under the auspices of the Durham VA Medical Center.
 - a. Local DVAMC memorandum "Authorization to Use, Process, Store, or Transmit VA Sensitive Information Outside VA Owned or Managed Facilities" has been pre-filled out for each study team member who may transport the data and/or specimens off-site. This (these) forms are included with the IRB materials.
 - b. Containers (e.g., briefcase, bin) are labeled with the following notice (label placed on the outside of container):

NOTICE!!!

Access to these records is limited to: AUTHORIZED PERSONS ONLY. Information may not be disclosed from this file unless permitted by all applicable legal authorities, which may include the Privacy Act; 38 U.S.C. §§ 5701, 5705, 7332; the Health Insurance Portability and Accountability Act; and regulations implementing those provisions, at 38 C.F.R. §§ 1.460 – 1.599 and 45 C.F.R. Parts 160 and 164. Anyone who discloses information in violation of the above provisions may subject to civil and criminal penalties.

III. Data and/or specimens will be transmitted to other VA sites using the following method(s):

A. Data

Data are de-identified and thus will be sent via unencrypted e-mail or unencrypted disk (encryption is optional).

Data are coded or contain identifiers and thus will be sent securely from other VAs to the Durham VA using a VA-approved travel scanner, scanned as an image file on a QUERI staff member's VA-issued, FIPS 140-2 encrypted laptop. The file will be uploaded to a HSR&D secure server when back in Durham. If the VA network is available at the participating VA and QUERI staff laptops can successfully access the network, the file will be uploaded while at the site. If wi-fi is available at the site or the hotel where QUERI staff are staying, the file will be uploaded securely through VPN to the Durham VA HSR&D server. If the travel scanner and secure transmission is not available, the paper data will be sealed in a in a VA business-reply envelope and sent to the Durham VA.

B. Specimens

Specimens are de-identified and thus will be sent via standard carrier (tracking is optional).

Specimens are coded or contain identifiers and thus will be sent via VA-authorized carrier with tracking.

IV. Data and/or specimens will be transported to non-VA/VHA sites (e.g., academic affiliates, laborato-ries, etc.) using the following method(s):

A. Data

Data are de-identified and thus will be sent via unencrypted e-mail or unencrypted CD.

Data are coded or contain identifiers and thus will be sent via > using VA—approved carrier with tracking.

Data are coded or identified and will be uploaded to sponsor website using electronic case report form (eCRF)

B. Specimens

Specimens are de-identified and thus will be sent via standard carrier (tracking is optional) or will be hand-delivered by research study personnel. Specify method of delivery:

Specimens are coded and thus will be sent via VA-approved carrier with tracking or will be hand-delivered by research study personnel. Specify method of delivery:

In accordance with the HIPAA and the Privacy Act, for any coded or identifiable data or specimens released from the Durham VAMC (with the exception of Limited Data Sets), an Accounting of Disclosure (AOD) will be maintained (e.g., in a database or spreadsheet) that includes the participant's name, date of the disclosure, description of the nature of the Individually Identifiable Information (III) disclosed, purpose of each disclosure, and the name and address of the person/agency to whom the disclosure was made.

7. Risk Mitigation Strategies:

Data are fully de-identified (stripped of HIPAA 18 and study ID/code) before being shared outside of Durham VAMC.

Specimens are fully de-identified (stripped of HIPAA 18 and study ID/code before being shared outside of Durham VAMC.

Direct identifiers will be maintained separately from data and or specimens by using a code to "identify" subjects. In a separate database (i.e., a "linking" or "cross-walk" database) this code will be linked to identifying subject information.

The subjects' right of privacy and the confidentiality of the protected health information will be guarded through strict controls and safeguards for access of the data to members of the research team. All study data will be stored on VA servers maintained by OI&T staff to comply with VA information security requirements. This includes study tracking and Datstat Illume survey databases on server OITDURSQLRESCH.VA.GOV, project shared document folder OITDURHSMSMB601.va.gov\Durham_HSRD_R and vhadurhsrd-sas1.v06.med.va.gov (SAS server temporary storage).Access to database and file systems is granted to research personnel via membership in Active Directory security groups created by OI&T and limited to individuals on the IRB staff listing. Members are removed from the security group when they no longer require access to study data. Data that will be temporarily stored on a VA-issued laptop will be stored in a FIPS-140-2 encrypted hard-drive. Only VA approved staff will have access to the data file for data analysis. The PI will have ultimate responsibility of access to the data. Furthermore, data will be kept in accordance with VA records control schedule.

Other, specify:

8. Suspected Loss of VA Information:

Should any incident such as theft or loss of data, unauthorized access of sensitive data or non-compliance with security controls occur it will be immediately reported according to VA policy. All incidents regarding information security/privacy incidents will be reported to the ISO and PO within 1 hour of acknowledgement of issue and done so using the VHADUR Research Events Report e-mail group ([contact]).

9. Reporting of Results:

Reporting of results, such as in scientific papers and presentations, will never identify individual subjects. Data will be presented in aggregate and individual-level data will not be published.

Other results reporting plan, describe:

10. Future Use of Data:

Data will be retained for future use. This is described elsewhere in the protocol and is noted in the HIPAA authorization.

Future Use of data is optional (i.e., not required by the research subject).

Future Use of data is required for participation in the study.

 \boxtimes No future use of data is currently planned.

11. Use of Mail Merge Technology N/A

Mail merge programs will be used to generate letters and/or address labels for mailings to potential or already enrolled research subjects. The study team is aware that to reduce risk of mail merge related privacy incidents, use of mail merge programs requires a 25% accuracy check to verify that (potential) research subject name and mailing address are properly "matched". If discrepancies are found, a 100% accuracy check is required before letters may be mailed.

References

Provide references, if applicable.

REFERENCES

- **3.** CDC grand rounds: public health practices to include persons with disabilities. *MMWR. Morbidity and mortality weekly report.* Aug 30 2013;62(34):697-701.
- 4. Roethlisberger FJD, W.J. Management and the worker. Cambridge, MA: Harvard University Press; 1939.
- 5. Hasenfield Y. Human Service Organizations. Englewood Cliffs, NJ: Prentice-Hall; 1983.
